8.1.4.4. Standards and Procedures for Stopping the Trial

Trial discontinuation refers to a situation in which the clinical study is not completed according to the protocol and all related clinical studies are stopped midway through the trial. Under all of the following conditions, with the exception of 5), will trigger mutual discussion between the sponsor and the investigator to determine whether or not to terminate the trial.

- 1) In the event that a serious safety concern arises during the course of the clinical trial the trial should be promptly terminated;
- 2) The trial should be discontinued when significant errors in the protocol are identified during the course of clinical studies, or when serious deviations in the implementation of the protocol make it difficult to evaluate the efficacy of the product;
- 3) The trial should be discontinued if the product is found to show sub-par efficacy or even complete inefficacy and is determined to be of no clinical value during the course of clinical research.
- 4) The trial is terminated upon the sponsor's request (e.g., due to funding issues, administrative reasons, etc.);
- 5) The trial is ordered to be terminated by the National Medical Products Administration

(NMPA) for any relevant reasons.

Early discontinuation of the trial must be agreed upon in writing by the principal investigator and the sponsor, and all trial data should be retained for reference purposes.

8.1.4.5. Enrollment Timetable

A subject may be enrolled upon obtaining confirmation that a signed informed consent form has been obtained, that the subject meets all entry criteria, and that the subject does not meet any exclusion criteria.

8.1.4.6. Expected Overall Duration of the Clinical Trial and Underlying Reasoning

In accordance with the relevant NMPA regulations on medical devices, this clinical study is scheduled to be conducted simultaneously at multiple qualified investigational centers across mainland China. Considering the patient volume at each center, the feasibility of implementing the protocol's inclusion and exclusion criteria, and the complexity of obtaining informed consent, the enrollment period is estimated to be 20 months. Mandatory CTA imaging follow-up will be performed at 30 days, 6 months, and 12 months post-operatively. A clinical summary will be prepared upon completion of the 12-month follow-up, and the 1-year clinical results will be submitted to the NMPA for review. Long-term follow-up will then continue from the 2nd to the 5th year; each subject will be followed for a total duration of 60 months. It is projected that the first subject will be enrolled in April 2024, and the final subject will be enrolled in December 2025. The overall study will be completed upon finalizing the 60-month follow-up of the last enrolled subject, which is estimated to occur in December 2030.

8.1.4.7. Expected Duration of Participation for Each Subject

For each subject, it is expected to take 60 to 62 months from the time of screening to performance of the procedure and the end of postoperative follow-up.

8.1.4.8. Number of Subjects Required for the Clinical Trial

The targeted number of valid cases for this study is 72. Considering a dropout rate of 20%, the total sample size is set at 90.

8.1.5. Primary Endpoints

Rate of all-cause mortality and major stroke within 12 months after surgery. All-cause mortality includes cardiac death, non-cardiac death, and death of unknown cause. Major stroke

is defined as a modified Rankin Scale (mRS) score ≥ 2 at 90 days after stroke onset (see Appendix 2).

Calculation formula: (Number of cases with all-cause mortality or major stroke at 12 months postoperatively / Total number of treated subjects) $\times 100\%$

8.1.6. Secondary Efficacy Endpoint

- (1) Rate of immediate technical success following surgery. Immediate technical success is defined as successful delivery of the aortic and branching stent graft conveyors to their predetermined positions, accurate positioning and successful deployment of the stent, safe removal of the delivery device outside the body, and the absence of Type I and III endoleaks per imaging studies conducted at the end of the procedure with all branching stents patency.
- (2) Rate of aortic aneurysm progression under control. Maximum increase in the diameter of the aortic aneurysm was ≤ 5 mm when compared with preoperative aortic aneurysm as of a 12-month postoperative CTA review.
- (3) Incidence of Type I or Type III endoleaks. Intraoperative, 1-month, 6-month, and 12-month DSA or CTA imaging studies showing endoleaks. Intraoperative endoleaks subject to adjuvant treatment are not recorded. Endoleaks occurring after the completion of the procedure followed by one or more endoleaks occurring in the same subject at different follow-up stages that were not treated are counted as a single instance.
- (4) Incidence of aortic covered stent graft displacement. CTA examination will be performed at 1, 6, and 12 months post operation to determine if the stent has migrated, and evaluations will be recorded for both the main and branch stents. Displacement is defined as a displacement of more than 10 mm in the aortic and branch stent grafts at follow-up time points compared with the 30-day postoperative reference imaging.
- (5) Postoperative branch vessel patency rate. CTA examinations will be performed at 1, 6, and 12 months post-operation to evaluate branch vessel reconstruction and assess for occlusion, stenosis, or in-stent thrombosis.

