In recent years, the development of fenestrated and branched stent grafts has provided novel devices and approaches for aortic arch pathologies⁷⁻⁹, substantially reducing the high mortality associated with open surgery (14% vs. 8%)^{7,10-13}. Endovascular intervention features minimal trauma, fewer complications, lower mortality, and faster postoperative recovery, enabling active treatment for elderly patients or those with cardiac, pulmonary, hepatic, or renal insufficiency. Currently, endovascular repair has become the first-line treatment for anatomically suitable patients with arch disease who are ineligible for open surgery. In routine clinical practice, due to the lack of mature, widely applicable multi-branched endovascular grafts for aortic arch reconstruction, off-label techniques such as parallel stent grafting and fenestration are commonly adopted to treat aortic arch lesions with standard aortic stent grafts. The parallel stent technique preserves branch perfusion and extends the landing zone by deploying small parallel stents (chimney stents) at the junction of arch branch vessels and the main aortic stent graft; nevertheless, gaps between the main graft and chimney stents carry a long-term risk of endoleak. Fenestration can be performed via in-vitro or in-situ approaches. In-vitro fenestration suffers from inaccurate alignment, while in-situ fenestration avoids positioning errors but still has limitations, including the risk of embolic debris from

fenestration and inapplicability to severely tortuous anatomies. With continuous technological innovation, branched stent graft technology—especially multi-branched endovascular aortic arch reconstruction—has emerged as the future direction, owing to its conformity to physiological anatomy and hemodynamics^{14–18}.

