9.2. Analysis Sets

The trial's statistical analysis will be conducted on the basis of the following analyzed populations,

which need to be clearly defined before the statistical analysis begins, and in this trial they include:

1. Full Analysis Set (FAS): Refers to the subject set that is as close as possible to intention-to-treat (ITT) principles, which is derived from all randomized subjects with minimal and reasonable censoring, and contains all subjects who have been subject to randomization and have previously used an investigational device. The FAS will be used for the evaluation of primary and secondary indicators.

2. Per Protocol Set (PPS): All patients showing good compliance with the trial protocol, good adherence, completion of the treatment specified in the trial protocol and no deficiencies in key efficacy indicators. The PPS will be used for the evaluation of primary and secondary indicators.

3. Safety Set (SS): All subjects who used an investigational device following randomization and underwent a safety evaluation. The SS will be is used for an analysis of safety indices.

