4) Secondary Endpoints

Technical success immediately post-procedure, aortic aneurysm progression control rate, incidence of Type I or Type III endoleak, incidence of aortic stent graft migration, postoperative patency rate of branch vessels, incidence of conversion to open thoracic surgery or secondary interventional procedure, major adverse event rate within 30 days post-operation, aortic aneurysm-related mortality at 12 months post-operation, incidence of serious adverse events, and incidence of device-related adverse events.

Statistical description shall be performed for secondary efficacy indicators, with frequencies and percentages calculated. FAS (Full Analysis Set) and PPS (Per Protocol Set) analyses shall also be conducted.

Statistical description shall be performed for secondary safety indicators, with frequencies and percentages calculated. The SS (Safety Set) analysis shall be adopted as the primary approach.

The Kaplan-Meier method shall be used to estimate the survival rate and its 95% confidence interval, with Kaplan-Meier curves plotted accordingly.

Descriptive statistical analysis shall be performed for the changes of all laboratory parameters before and after the trial. All adverse events occurring during the trial shall be recorded in detail; descriptive statistical analysis of adverse events shall be conducted with a list attached.

In addition to the above statistical methods, detailed and additional exploratory analyses may be required, which shall be confirmed in the Study Report and Statistical Analysis Plan (SAP)..

9.5. Statistical methods for all data, including the handling of missing, unused or erroneous data (including premature discontinuation and withdrawal) and inconsistent data.

A Statistical Analysis Plan (SAP) shall be developed prior to study initiation. After database lock, statistical analysis shall be performed in accordance with the SAP, and a statistical analysis report shall be generated based on the results.

(1) Handling of missing data: Missing data shall be handled according to the analysis set in which they are included. Missing data for the primary endpoint in the Full Analysis Set (FAS) shall be classified by reason as follows:

Missing data clearly due to unsatisfactory efficacy: loss to follow-up or missing primary efficacy data resulting from adverse events, death, etc., related (or possibly related) to the investigational device or aortic dissection.

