Missing data not attributable to unsatisfactory efficacy: loss to follow-up, failure to complete assessments, or other reasons such as force majeure (e.g., epidemic restrictions) resulting from adverse events, death, etc., unrelated to the investigational device or aortic dissection.

For the first category of missing data, worst-case imputation shall be used in both the FAS and Per Protocol Set (PPS), treated as “12-month postoperative failure”. For the second category of missing data, three imputation methods shall be applied separately, followed by sensitivity analysis:

1) Best-case imputation: all treated as “12-month postoperative success”; 2) Worst-case imputation: all treated as “12-month postoperative failure”; 3) Tipping-point analysis: the imputation proportions of success and failure in the two groups shall be varied iteratively to comprehensively demonstrate whether the study meets the statistical hypothesis under different scenarios and to identify the tipping point at which the conclusion changes.

No statistical imputation shall be used for missing data of other endpoints.

(2) Handling of inconsistent data: During data management, logical checks shall be performed on the database. Inconsistent data shall be queried via data query forms sent to investigators. Inconsistent data shall be resolved based on written responses from investigators. The database shall not be locked until all inconsistent data has been resolved.

(3) Handling of erroneous data: During data management, quality control should be conducted on the database. Erroneous data shall be identified and queried via data queries (Query). Errors shall be corrected based on investigators' responses, and queries shall be closed only after confirmation from investigators. The database shall not be locked until all erroneous data has been corrected.

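### Aneurysm control is tied to the 12-month CTA and imputation is barred, so rupture, conversion or re-treatment before month 12 has no stated route to failure

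*Protocol*

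**What the plan says.** Section 8.1.6(2) of the protocol, repeated in the protocol summary, defines the endpoint as "Maximum increase in the diameter of the aortic aneurysm was ≤ 5 mm when compared with preoperative aortic aneurysm", assessed "as of a 12-month postoperative CTA review". The three items that follow it, on endoleak, graft displacement and branch patency, each name the 1-, 6- and 12-month images. Item (2) names only month 12.

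Section 9.4.2 gives the analysis: "Statistical description shall be performed for secondary efficacy indicators, with frequencies and percentages calculated". Section 9.2 assigns the analysis set: "The FAS will be used for the evaluation of primary and secondary indicators". The per-protocol set is used as well. No formula or denominator is given for aneurysm control, whereas Section 8.1.5 divides the primary endpoint by all treated subjects.

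Section 9.5 sets the missing-data rule. For the primary endpoint it treats "loss to follow-up or missing primary efficacy data resulting from adverse events, death, etc" as a class of missing data and, when related to the device or the aortic disease, scores it as failure under the name of worst-case imputation. For everything else it says: "No statistical imputation shall be used for missing data of other endpoints".

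**The concern.** A subject whose lesion ruptures fatally before month 12 has no 12-month diameter, and a subject converted to open surgery may have none that can be evaluated. In the protocol's own vocabulary such a subject is missing, and scoring the subject as a failure would be imputation, which is barred for this endpoint. A subject whose aneurysm grows, is re-treated and is back within 5 mm at month 12 meets the definition of control.

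These are the subjects in whom control failed most clearly. If they leave the calculation or count as successes, the rate describes subjects who reached the 12-month scan and not everyone who was treated, and it leans towards the device. No other endpoint feeds these events into the rate. Aneurysm-related death is a separate safety endpoint (Section 8.1.7(3)). The conversion and reintervention endpoint (Section 8.1.7(1)) is worded around new-onset dissection, so re-treatment for aneurysm growth is not named there. The 12-month results go to the regulator (Section 8.1.4.6).

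**Working it through.** **The plan's own figure.** Section 8.1.4.8 gives 72 valid cases and 20% dropout: 72 / (1 − 0.20) = 90, which reproduces the stated total. The protocol states no expected control rate, so the effect can only be shown by counting under assumptions.

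**Illustration 1: small counts.** Inputs:

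- 90 treated (Section 8.1.4.8).
- 7 deaths before the 12-month scan. This is an assumption: 8% × 90 = 7.2, rounded. The 8% is the lower mortality figure in Section 5, which gives no time horizon.
- 3 of the 7 deaths from rupture of the treated lesion (assumed).
- 3 survivors re-treated for growth and within 5 mm at month 12 (assumed).
- 1 other survivor with growth above 5 mm at month 12 (assumed).
- No conversions and no other missing scans (assumed).

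Scanned at month 12: 90 − 7 = 83. Within 5 mm: 83 − 1 = 82.

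| Counting rule | Rate | Failures | Gap to first row |
|---|---|---|---|
| Scanned subjects only, as written | 82/83 = 98.8% | 1 | – |
| Rupture deaths added as failures | 82/(83 + 3) = 82/86 = 95.3% | 4 | 3.4 points |
| Re-treated growth also a failure | (82 − 3)/86 = 79/86 = 91.9% | 7 | 6.9 points |

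About half of the larger gap comes from the three re-treated subjects.

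**If the denominator were all treated subjects.** The definition as written gives 82/90 = 91.1%. With re-treated growth as failure it gives 79/90 = 87.8%. The loss of subjects without a scan no longer raises the rate, but 3/90 = 3.3 points from the re-treated subjects remain.

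**Illustration 2: larger counts.** Assume 90 treated, 5 with growth above 5 mm at month 12, E subjects without a scan because of death, rupture or conversion, and R re-treated for growth and within 5 mm at month 12.

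- Scanned only: (85 − E)/(90 − E).
- Events as failures, all treated: (85 − E − R)/90.

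| E | R | Scanned only | Events as failures | Gap |
|---|---|---|---|---|
| 5 | 0 | 80/85 = 94.1% | 80/90 = 88.9% | 5.2 points |
| 9 | 3 | 76/81 = 93.8% | 73/90 = 81.1% | 12.7 points |
| 18 | 5 | 67/72 = 93.1% | 62/90 = 68.9% | 24.2 points |

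The last row is an extreme: it attributes the whole 20% dropout allowance (0.20 × 90 = 18) to such events. The pattern matters more than the size. The scanned-only rate stays between 93% and 94% while the number of early failures more than triples.

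**The case against.** **The denominator.** A reader might infer that early failures certainly drop out and can never lower the rate. The protocol does not say so. It gives no denominator, it assigns secondary endpoints to a set meant to be close to intention-to-treat, and the analysis plan may settle the matter. If the rate is controlled subjects over the full analysis set, a subject without a scan lowers it. This stands, and it makes the inflation from missing scans conditional. It does not close the point: counting such subjects as not controlled is what Section 9.5 calls imputation and bars here, and re-treated subjects would still count as controlled.

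**Earlier scans.** A reader might also infer that the 6-month diameters are ignored. The definition speaks of a maximum increase, which can be read as the largest increase on any scan up to month 12. On that reading, growth seen at 6 months fails even if later re-treated. The single-scan reading is the more natural one, given how items (3) to (5) are worded, but the text allows both. The wider reading still does not classify rupture, death or conversion.

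**The counts.** Section 5 gives an average natural growth of 0.1 cm a year, so growth above 5 mm within a year is more than five times that average. The number re-treated for growth could be small, and without those subjects the gap in the first illustration is 3.4 points and not 6.9.

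**Coverage elsewhere.** All deaths enter the primary endpoint, aneurysm-related death has its own endpoint, and Type I and III endoleaks are counted separately. This stands, and it limits what is at stake to how one secondary rate is read. It is also a reason not to turn that rate into a broad composite.

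**Conclusion.** The concern holds in a limited form. As worded, the endpoint and the ban on imputation leave rupture, aneurysm-related death and conversion without an evaluable scan before month 12 with no stated route to failure, and on the natural reading they let a subject re-treated for growth count as controlled. For these subjects the direction favours the device. Leaving out deaths from other causes is a choice of what is being estimated and not clear inflation.

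The size cannot be derived from the documents. It is roughly 3 to 7 points under the first set of assumed counts and more if more subjects lack a scan for these reasons. Neither set of counts is a forecast, and the 8% is not a 12-month mortality estimate.

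A reader might infer that the trial's main result is compromised. It is not: the endpoint is secondary and descriptive, with no test or success threshold, and the primary conclusion is unaffected. The change is worth making because it is cheap and removes a bias that can be foreseen.

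**What to change.** In Section 8.1.6(2) and the protocol summary:

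- State that control requires an increase of no more than 5 mm over the preoperative diameter on every scheduled CTA through month 12. Section 8.2.2 already collects aortic diameter at 30 days and 6 months.
- State that rupture of the treated lesion, death from aneurysm rupture, or conversion or reintervention for aneurysm growth before month 12 counts as not controlled by definition. The rule in Section 9.5 against imputation can then stand.
- Report the rate over all treated subjects beside the rate among those with a 12-month CTA, with deaths from other causes and missing scans as separate counts.
- Do not fold in all procedure-related deaths, or reintervention for leak without growth. The first would score a fatal periprocedural stroke as failed aneurysm control, and both overlap with Sections 8.1.6(3) and 8.1.7(3).

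The cost is wording in the protocol and the analysis plan, with no new visits or scans. The case report form must show the reason for any conversion or reintervention. The downside is a slightly less favourable reported rate.

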8.1.7. Secondary Safety Endpoints

- (1) Rate of conversion to thoracotomy or secondary intervention. Whether subjects require

conversion to open thoracic surgery or secondary interventional procedures due to new-onset aortic dissection caused by the index procedure.

- (2) Rate of major adverse events occurring within 30 days after surgery. Refers to all-cause mortality, myocardial infarction, ischemic stroke or respiratory failure occurring within 30 days after surgery. More specifically, myocardial infarction refers to a drastic reduction or complete interruption of the coronary blood supply due to coronary artery disease, resulting in severe and prolonged acute ischemia of the corresponding myocardium, leading to necrosis of cardiomyocytes. Ischemic stroke refers to the end result of necrosis of brain tissue caused by narrowing or occlusion of the arteries supplying blood to the brain or insufficient blood supply to the brain. Respiratory failure is defined as a state resulting in significantly prolonged intubation, tracheotomy, deterioration of lung function, or other fatal outcomes.
- (3) Rate of aortic aneurysm-related mortality at 12 months post operation. Refers to mortality caused by a ruptured aortic aneurysm or endovascular interventional treatment.
- (4) Incidence of severe adverse events. Refers to an event that occurs during the clinical trial that results in mortality or serious deterioration in patient health, including a fatal illness or injury, a permanent defect in body structure or body function, or an event that requires medical or surgical intervention to avoid one or more permanent defects in body structure or body function.
- (5) Incidence of device-related adverse events. Device-related adverse events refer to an adverse medical event related to the use of a device that occurs during the course of the clinical trial. However, a distinction should be made with respect to normal postoperative stress response, such as fever and chest and back discomfort, which, in the judgment of the investigator, need not be recorded as an adverse event. Recording device-related adverse events will be applicable for conditions that are deemed by the investigator to be definitely related, possibly related, or of indeterminate relationship, to the test device.

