- Concomitant medication records: medications relevant to the evaluation of the investigational device (including anticoagulants, antiplatelet agents, antihypertensives, lipid-lowering drugs, hypoglycemic drugs, antibiotics, etc.); and medications administered for underlying diseases, concomitant diseases, or adverse events.
- Adverse event records: all adverse events starting from Visit V2.
- In the event of a stroke in a subject, the modified Rankin Scale (mRS) score shall be collected at 90 days after the stroke onset.
- If feasible, laboratory data obtained within 15 days prior to subject enrollment (before signing the informed consent form), as well as aortic CTA, cerebral CTA or Magnetic Resonance Angiography (MRA), echocardiography, and 12-lead ECG data obtained within 30 days prior to signing the informed consent form, may be used for baseline assessment without repeat testing.
- Long-term follow-up CTA data shall be collected at postoperative Years 2, 3, 4 and 5 (± 30 days), with records of adverse events and concomitant medications related to adverse events.*Relevant examinations and data collection shall be performed only in patients randomized to the test group.

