14.4.3. Potential Adverse Events

Allergies, aortic dissection enlargement, aortic dissection rupture, arterial thrombosis, arterial injury, arterial perforation, arteriovenous fistula, pseudoaneurysm, hemorrhage/hematoma, bowel syndrome, pulmonary syndrome, heart failure/myocardial infarction, intermediate surgery, death, edema, sexual dysfunction, fever, renal insufficiency/failure, wound syndrome, air embolism and device complications, including: incorrect release position, stent migration, stent breakage, endoleak and coating rupture.

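### Type I/III endoleaks treated during the procedure are ordered not to be recorded, which conflicts with adverse event recording and leaves no efficacy endpoint showing how often the device needed help to seal

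*Protocol*

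**What the plan says.** Protocol section 8.1.6, item (3), defines the incidence of Type I or Type III endoleak; the Trial Protocol Summary repeats it. The assessment times are "Intraoperative, 1-month, 6-month, and 12-month DSA or CTA imaging studies showing endoleaks". Two rules follow. The first is that "Intraoperative endoleaks subject to adjuvant treatment are not recorded". The second concerns leaks after the procedure: repeats "occurring in the same subject at different follow-up stages that were not treated are counted as a single instance". No denominator is given.

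Four other places bear on the point:

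- **Section 8.1.6, item (1).** Technical success requires, among other things, "the absence of Type I and III endoleaks per imaging studies conducted at the end of the procedure".
- **Section 8.1.7, item (1).** The re-intervention endpoint is conversion to open surgery or "secondary interventional procedures due to new-onset aortic dissection caused by the index procedure".
- **Section 8.2.1, notes to the chart.** The adverse event record covers "all adverse events starting from Visit V2". Visit 2 is the day of surgery.
- **Section 14.4.3.** The device complications listed among potential adverse events include "stent migration, stent breakage, endoleak and coating rupture".

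**The concern.** How often a modular branched graft seals without extra treatment is a basic performance property. The endpoint that should describe sealing looks at intraoperative imaging and then sets aside the intraoperative leaks that needed treatment. The instruction is worded as one about recording, not only about what enters the rate.

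Two things are at stake. First, sites may follow different instructions: one may leave a treated leak out because of 8.1.6, while another reports it as an adverse event because of 8.2.1 and 14.4.3. The adverse event tables would then partly reflect how each site read the protocol. Second, reported sealing performance is favourable by construction, because a leak that was seen and sealed before the final angiogram leaves the endoleak incidence and technical success unchanged.

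**Working it through.** **Step 1. Follow one subject through the endpoints.** Take a subject with a Type I leak on intraoperative imaging that is treated and is gone on the final angiogram.

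| Endpoint or record | Is the leak visible? | Reason |
|---|---|---|
| Endoleak incidence, 8.1.6 (3) | No | Treated intraoperative leaks are not recorded |
| Technical success, 8.1.6 (1) | No; its leak component is met | Judged at the end of the procedure |
| Re-intervention, 8.1.7 (1) | No | Tied to new-onset dissection |
| Device-related adverse events, 8.1.7 (5) | Depends on the site | 8.2.1 and 14.4.3 point to recording, 8.1.6 (3) against |
| Visit 2 data (8.2.2) and source records (section 16) | In part | DSA data, surgical records and materials used are kept |

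**Step 2. Can the last row replace an endpoint?** Only partly. Section 10.2 builds the eCRF from the data points that the protocol specifies, and the Visit 2 list in 8.2.2 names neither endoleak nor adjuvant treatment. Materials used do not cleanly separate rescue from plan, because section 7.3 (2) allows an additional aortic extension graft on anatomical grounds.

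**Step 3. Size.** The protocol states no endoleak figure to reproduce. The only figure used is the planned enrolment, which does reproduce from 8.1.4.8: 72 / (1 − 0.20) = 90. The event counts below are assumptions.

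Let L = 4 subjects have a later leak and I further subjects have a leak treated during the procedure, with no overlap. The endpoint is L/90; subjects with any leak are (L + I)/90. Intervals are exact (Clopper-Pearson) 95%.

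| I (assumed) | Endpoint as written | Subjects with any Type I/III leak |
|---|---|---|
| 0 | 4/90 = 4.4% (1.2 to 11.0) | 4/90 = 4.4% (1.2 to 11.0) |
| 4 | 4/90 = 4.4% | 8/90 = 8.9% (3.9 to 16.8) |
| 9 | 4/90 = 4.4% | 13/90 = 14.4% (7.9 to 23.4) |
| 18 | 4/90 = 4.4% | 22/90 = 24.4% (16.0 to 34.6) |

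On 72 subjects the endpoint is 4/72 = 5.6%, against 8/72 = 11.1%, 13/72 = 18.1% and 22/72 = 30.6%. If instead all 4 later leaks fall in subjects already treated during the procedure, the last two rows on 90 become 9/90 = 10.0% and 18/90 = 20.0%. In every case the endpoint does not move with I.

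**Step 4. The counting rule for later leaks.** Suppose 6 of 90 subjects have leaks, with untreated repeats only. Merging repeats gives 6 instances, and 6/90 = 6.7% is also the proportion of subjects, so the stated rule does no harm there. The two counts differ only if a leak is treated, recurs, and is then counted again, a case on which the text is silent.

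**The case against.** The strongest reply is that the sentence sits inside the endpoint definition, beside its counting rule, and is most naturally read as saying what does not count toward that endpoint. On that reading the data are still captured. Visit 2 collects DSA data, surgical records, adverse events and device defects; section 8.1.9 calls for a core laboratory to evaluate imaging; section 16 requires all materials used to be documented; and adverse events are described and listed (9.4.2). Judging technical success at the end of the procedure is an explicit definition, not a mistake. Nor is it certain that a leak sealed during the procedure is an adverse event merely because 14.4.3 lists endoleak as a potential one.

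Much of this stands. A reader might infer that the trial cannot show the need for adjuvant sealing at all, or that the information is lost for good at database lock. The documents do not support either: the records above exist, and section 10.12 provides for a co-signed unlock when an error has significant impact. A reader might also infer that the incidence is not a proportion of subjects. That is not supported either: the single-instance rule equals a subject count for untreated repeats, and the general principles in 9.4.2 call for number and percentage of subjects. Double counting of treated recurrences would have to be read into silence, and detail of that kind, like the denominator, is commonly left to the SAP.

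What the reply does not remove is the wording. It says not recorded, where not counted would have served, and it stands against the adverse event rule. Even on the milder reading, no efficacy endpoint reports these leaks.

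**Conclusion.** The point holds in a narrow form. The recording instruction in 8.1.6 (3) conflicts with 8.2.1 read with 14.4.3. Neither endoleak incidence nor any other defined efficacy endpoint, nor the re-intervention endpoint, shows how often adjuvant treatment was needed to seal. The number could be recovered only in part from DSA data, surgical records and adverse event listings.

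The size is unknown. The illustration (4.4% reported against 8.9% to 24.4% with any leak) rests on assumed counts, 90 subjects and no overlap. It shows only that the endpoint is insensitive to leaks treated during the procedure and that the direction favours the device.

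The counting rule is a matter of clarification, not an error. The endpoint is secondary and descriptive, so the primary analysis, alpha and sample size are untouched. The change is worth making because it is cheap and is best made before sites record their procedures.

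**What to change.** In section 8.1.6 (3) and in the Trial Protocol Summary, replace the instruction not to record. State that intraoperative Type I/III endoleaks given adjuvant treatment are recorded at Visit 2 together with that treatment, are not counted in the follow-up incidence, and are reported on a separate line as number and percentage of subjects. Add the matching item to the Visit 2 list in 8.2.2 so that it reaches the eCRF.

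State in the same amendment whether such a leak is also to be entered as an adverse event, so that 8.1.6, 8.2.1 and 14.4.3 give sites one instruction. The definition of technical success can stay as it is.

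As a clarification, define the incidence as subjects with at least one Type I/III endoleak over subjects with evaluable imaging, at each time point and cumulatively. Instances, including recurrence after treatment, can be listed as a supplement.

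The cost is one eCRF item filled from imaging already taken, a short protocol amendment with matching SAP text, and one less favourable line in the report.
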